2.2.2 Secondary Outcomes

- Parental report of provider-diagnosed AD - This parental report of AD question has been validated previously by our group and was found to have adequate sensitivity and specificity during our trial planning activities.³⁹

- AD as diagnosed by the Children's Eczema Questionnaire (CEQ) – The CEQ is a newly developed 2-question parental questionnaire based on the U.K. Working Party criteria.⁴⁰ This instrument will be used to capture dyads not evaluated by their provider or lost to follow-up (Appendix A).
- Parental report of sleep loss of the infant reported as average parental report of days per week of disrupted sleep in their infant (1 week recall) measured at 12 and 24 months.
- Any prescription topical medication use or over-the-counter hydrocortisone usage recorded by parent or recorded from records review by research coordinator at 24 months.
- Asthma risk questions from the modified Asthma Predictive Index (mAPI) that uses family history, atopic dermatitis, sensitization history, and wheezing episodes to predict the development of asthma measured by parental report.⁴¹ This will be recorded as either high risk or low-risk at 12 and 24 months following mAPI criteria (Appendix B). Wheezing episodes will be assessed using the International Study of Asthma and Allergies in Childhood (ISAAC) questionnaire.
- Parental report of immediate food allergy symptoms – A general question regarding the development of red rash/hives, lip swelling, wheezing, abdominal pain, or vomiting that developed in the infant within two hours of eating a food.
- Parental report of a provider diagnosis of food allergy that was confirmed by prick testing or IgE blood test.
- One question global health status from the PROMIS Pediatric Global Health (PGH-7) instrument.⁴² (Appendix C)
- In infants who develop AD, a logic model in our survey instrument will ask the following parental reported outcomes in the 12- and 24-month questionnaires:
 1. Time to onset of AD as measured by parental report of eczema age of onset.
 2. Time to onset of AD as measured by provider-recorded date of first diagnosis retrieved from record review of chart by research coordinator.
 3. AD symptom severity as reported by the Patient-Oriented Eczema Measure (POEM) instrument⁴³ (Appendix D).
 4. Parent-reported global severity of eczema assessment – mild, moderate, severe

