6.2 Intermediate Contacts

Contact 2, Infant Age 3 Months ± 14 days

Quarterly contact sent to parents by text message and/or e-mail.

- Confirm or update contact information.
- Confirm or update primary care clinic where infant receives care.
- Parental report of AD or eczema diagnosis by a clinician.
- Average daily usage of emollient
- Parental report of skin product-related adverse events and any serious adverse events
- Intervention group only: record emollient supply and ship resupply if requested

Contact 3, Infant Age 6 Months ± 14 days

Quarterly contact sent to parents by text message and/or e-mail.

- Confirm or update contact information.
- Confirm or update primary care clinic where infant receives care.
- Parental report of AD or eczema diagnosis by a clinician.
- Average daily usage of emollient
- Parental report of skin product-related adverse events and any serious adverse events
- Intervention group only: confirm preferred emollient and ship resupply

Contact 4, Infant Age 9 Months ± 14 days

Quarterly contact sent to parents by text message and/or e-mail.

- Confirm or update contact information.
- Confirm or update primary care clinic where infant receives care.
- Parental report of AD or eczema diagnosis by a clinician.
- Average daily usage of emollient
- Parental report of skin product-related adverse events and any serious adverse events
- Intervention group only: record emollient supply and ship resupply if requested

Contact 5, Infant Age 12 Months - 4 weeks + 12 weeks

12 month questionnaire contact sent to parents by text message and/or e-mail.

- Confirm or update contact information.
- Confirm or update primary care clinic where infant receives care.
- AD or eczema diagnosis by a clinician.
- Parental report of skin product-related adverse events and any serious adverse events
- Skin care practices, adherence to intervention/control instructions
- Parental report of sleep loss
- Medication history
- Modified Asthma Predictive Index (mAPI) and International Study of Asthma and Allergies in Childhood (ISAAC) questionnaire
- Infant diet
- Food allergy questions, including parental report of clinician-diagnosed food allergies
- In infants who develop AD:
 - Parental report of AD age of onset
 - AD symptom severity using POEM
 - Parent-reported global severity of eczema
 - Infant Dermatology Quality of Life Instrument (IDQOL)
- Intervention group only: confirm preferred emollient and ship resupply

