2.7. Study Schema

Parentheses (•) indicate that a measure applies to a subset of participants, e.g. intervention arm only, or only children with diagnosed AD.

Table 3. Study schema

Schedule of events		Screening	Contact 1	Contact 2	Contact 3	Contact 4	Contact 5	Contact 6	Contact 7	Contact 8	Contact 9
Child age (months)		≤ 2	≤ 2	3	6	9	12	15	18	21	24
Procedures											
Consent		•	•								
Assessment of Eligibility (Inclusion/Exclusion criteria)		•									
Baseline	Demographics		•								
	AD Risk		•								
	Living Environment		•								
	Pet Ownership		•								
	Alternate Contact		•								
Provide/Update Contact Info			•	•	•	•	•	•	•	•	
Quarterly Contact	Confirm PCP		•	•	•	•	•	•	•	•	•
	AD diagnosis		•	•	•	•	•	•	•	•	•
	Study arm adherence		•	•	•	•	•	•	•	•	•
Choose and ship emollient (Intervention Group Only)		(•)		(•)		(•)		(•)			
Assessment of AE/SAE			•	•	•	•	•	•	•	•	•
Annual Questionnaire	mAPI and ISAAC					•					•
	CEQ					•					•
	UK Working Party					•					•
	Sleep loss					•					•
	Allergies					•					•
Study arm adherence						•					•

Chart Abstraction	Medication history						•				•
	PGH-7 Global Health						•				•
	Infant diet						•				•
	Emollient acceptability (Intervention Group Only)						(•)				(•)
	If infant develops AD: -AD age of onset -Global severity of AD -IDQOL -POEM						(•)				(•)
	AD or eczema diagnosis by HCP						•				•
	Intensity of AD						(•)				(•)
	Medication history						(•)				(•)
	Other allergy diagnoses						(•)				(•)
	Assessment of AE/SAE						•				•

3. Statistical Principles

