Over the last week, on how many days [nights, item 2] has your child's ...

... skin been itchy because of their eczema?

... sleep been disturbed because of their eczema?

... skin been bleeding because of their eczema?

... skin been weeping or oozing clear fluid because of their eczema?

... skin been cracked because of their eczema?

... skin been flaking off because of their eczema?

... skin felt dry or rough because of their eczema?

b) Lower mean score on the 30-point Infants' Dermatitis Quality of Life Index (IDQOL) where higher scores indicate more impairment¹². To score, sum the items below. A missing item will result in a missing response.

Over the last week, HOW SEVERE do you think your child's dermatitis has been? In other words, how red, scaly, inflamed or widespread.

4, Extremely Severe | 3, Severe | 2, Average | 1, Fairly Good | 0, No Eczema

Over the last week, how much has your child been ITCHING AND SCRATCHING?

3, All the time | 2, A lot | 1, A little | 0, None

Over the last week, what has your child's MOOD been?

3, Always crying, extremely difficult | 2, Very fretful | 1, Slightly fretful | 0, Happy

How many nights in the past week would you say your child's sleep was disturbed at night, not including routine feeding? 0-7

Over the last week approximately how much TIME on average has it taken TO GET your child OFF TO SLEEP each night?

3, More than 2 hours | 2, 1 to 2 hours | 1, 15 minutes to 1 hour | 0, 0 to 15 minutes

Over the last week, what was the TOTAL TIME that your child's SLEEP WAS DISTURBED on average each night?

3, 5 hours or more | 2, 3-4 hours | 1, 1-2 hours | 0, Less than 1 hour

Over the last week, has your child's eczema interfered with PLAYING OR SWIMMING?

3, Very much | 2, A lot | 1, A little | 0, Not at all

Over the last week, has your child's eczema interfered with them TAKING PART IN or ENJOYING OTHER FAMILY ACTIVITIES?

3, Very much | 2, A lot | 1, A little | 0, Not at all

Over the last week, have there been problems with your child at MEALTIMES because of the eczema?

3, Very much | 2, A lot | 1, A little | 0, Not at all

Over the last week, have there been problems with your child caused by the TREATMENT?

3, Very much | 2, A lot | 1, A little | 0, Not at all

Over the last week, has your child's eczema meant that DRESSING AND UNDRESSING the child has been UNCOMFORTABLE?

3, Very much | 2, A lot | 1, A little | 0, Not at all

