Over the last week, how much has your child having eczema been a problem at BATH TIME?

3, Very much | 2, A lot | 1, A little | 0, Not at all

10. Delayed onset of AD, with age of onset determined by

a) provider-recorded date of first diagnosis retrieved from record review of chart by research coordinator

[Field:] Date (or age of child in months) of first AD diagnosis in the chart

b) parental report of eczema age of onset to the nearest 3 months (based on quarterly contacts)

Note: For interval-censored analysis, these variables will use the date of visit/response and previous visit/response as the end and start of the interval, respectively.

11. Lower mean days of disrupted sleep in the past week for infants reported by parents at 12 and 24 months, taken from the single item (#4) in the IDQoL.

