Table Title	Population	Time Point(s)	Endpoint	Endpoint Type	Summary Statistics by Treatment Assignment
Breathing Problems	ITT	12m,24m	Ever wheeze	Binary(Y/N)	p%(x/n)
			Number of wheeze events over past year (cat)	Count	p%(x/n)
			Wheeze without cold	Binary(Y/N)	p%(x/n)
			Diagnosed asthma	Binary(Y/N)	p%(x/n)
			Asthma predictive index-Y/N (derived)	Binary(Y/N)	p%(x/n)
Allergies	ITT	12m,24m	Skin Prick Test or Blood test	Binary(Y/N)	p%(x/n)
			Food allergy symptoms	Binary(Y/N)	p%(x/n)
			Food exposure	Binary(Y/N)	p%(x/n)
Severity of symptoms and influence on quality of life	AD population	12m,24m	POEM score (0-28)	Continuous	n, mean, SD, Median, min, max
			IDQOL score (0-30)	Continuous	n, mean, SD, Median, min, max
	ITT	12m,24m	Parent-rated health status	Ordinal(1-5)	p%(x/n) n, mean, SD, Median, min, max
			Days of disrupted sleep in the past week	Count(0-7)	p%(x/n) n, mean, SD, Median, min, max
			Adverse reaction to skin product	Binary(Y/N)	p%(x/n)
Adverse events	ITT	12m,24m	Type	Categorical	p%(x/n)
			Ended	Binary(Y/N)	p%(x/n)
			Severity	Categorical	p%(x/n)
			Require HCP visit	Binary(Y/N)	p%(x/n)
			Diagnosis	Categorical	p%(x/n)
			AE Treatment-Y/N	Binary(Y/N)	p%(x/n)
			AE Treatment-name	Categorical	p%(x/n)
			SAE listing	Narrative	n/a
					p%(x/n)
Contact info change	ITT	Any time			p%(x/n)

Table 5. Exploratory analyses

Subgroup	Intervention cumulative incidence	Usual care cumulative incidence	Difference (risk difference) 90% CI	Difference in differences	Risk Ratio 90% CI	Difference (ratio scale)	P value for interaction
Family history of atopy							
Yes							
No							
Climate							
Dry							
Wet							
Domestic animals							
Any							
None							
Cat(s)							
Dog(s)							
Farmanimal(s)							
Sex							
Female							
Male							
Age at randomization							
Youngest							
Middle							
Oldest							
Emollient type used							
CeraVe							
Others							
None							

6. References

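### SAP 5.1 item 11 sources the all-infant disrupted-sleep endpoint from IDQOL, an instrument scheduled only for infants who develop AD

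*SAP*

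**What the plan says.** SAP 5.1 item 11 states the endpoint as "Lower mean days of disrupted sleep in the past week for infants reported by parents at 12 and 24 months" and gives its source as "taken from the single item (#4) in the IDQoL". SAP 5.4 refers back to 5.1 for the definitions of secondary endpoints. Item 10 of 5.4, the Poisson analysis of sleep days, names neither a source question nor a population, so item 11 is the operative definition.

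The fourth question in the IDQOL list (SAP 5.1, item 9b) is "How many nights in the past week would you say your child's sleep was disturbed at night, not including routine feeding", answered 0 to 7. It is the only wording for a disrupted-nights question anywhere in the SAP.

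IDQOL is a conditional instrument. Protocol 2.2.2 introduces it with "In infants who develop AD, a logic model in our survey instrument will ask the following parental reported outcomes". SAP Table 3 has the row "If infant develops AD: -AD age of onset -Global severity of AD -IDQOL -POEM", marked in parentheses, and its legend reads "Parentheses (•) indicate that a measure applies to a subset of participants, e.g. intervention arm only, or only children with diagnosed AD".

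Sleep is handled differently elsewhere. Table 3 has its own sleep-loss row, without parentheses, at 12 and 24 months. Protocol 6.2 lists "Parental report of sleep loss" at Contacts 5 and 9, outside the sub-list for infants with AD. SAP Table 4 puts "Days of disrupted sleep in the past week" in the ITT population as a count from 0 to 7, and puts POEM and IDQOL in the AD population.

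**The concern.** The definition that governs the analysis points to an instrument that most randomised infants are not scheduled to receive, while the schedule and the table plan treat the endpoint as universal. An analyst who follows item 11 to the letter would take sleep from the IDQOL block and compare arms among infants with AD.

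That comparison conditions on something that happens after randomisation and that the intervention is meant to change. The AD infants in the two arms need not be alike, because the intervention may have removed some kinds of case from one arm and not the other. Sleep gained because an infant never developed AD would be excluded by construction, although for a prevention trial that is the main route by which an emollient would be expected to help sleep.

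**Working it through.** **1. The passages side by side**

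| Place | Who has the sleep measure |
|---|---|
| SAP 5.1 item 11, population words | Infants, no AD restriction |
| SAP 5.1 item 11, source words | IDQOL item 4, so infants with AD |
| SAP Table 3, IDQOL row | Infants with AD (parentheses) |
| SAP Table 3, sleep-loss row | All (no parentheses) |
| Protocol 6.2, Contacts 5 and 9 | All |
| Protocol 2.2.2 | General secondary outcome, listed apart from the AD-only set |
| SAP 5.4 item 10 | No restriction stated |
| SAP Table 4 | ITT |

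Only the source words in item 11 tie sleep to the AD-only instrument.

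**2. Does the nights question belong to IDQOL?**

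Item maxima in the 9b list, in order: severity 4, itch 3, mood 3, nights 7, time to fall asleep 3, total time disturbed 3, then six items at 3 each.

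- As listed: 12 items, 4 + 3 + 3 + 7 + 3 + 3 + 6 × 3 = 41 points.
- Without nights: 11 items, 34 points.
- Without severity: 11 items, 37 points.
- Without both: 10 items, 30 points.

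Protocol 2.2.2 describes a 10-question instrument and the SAP a 30-point score. Only the last line matches both. By the plan's own figures the nights question is not one of the scored IDQOL items. Its wording does not mention eczema, and its 0 to 7 range matches the count in Table 4.

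**3. The plan's sample size, as denominator**

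Inputs from SAP 2.3: risks 24% and 16.8%, two-sided α = 0.05, power 80%.

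n per arm = [1.960 × √(2 × 0.204 × 0.796) + 0.842 × √(0.24 × 0.76 + 0.168 × 0.832)]² / 0.072² = 491, or 982 in total. The stated figure reproduces.

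**4. Size if item 11 is taken literally**

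- Control: 491 × 0.24 = 118. Intervention: 491 × 0.168 = 82. Total 200 of 982, or 20.4%. At full enrolment: 150 + 105 = 255 of 1,250.
- Detectable standardised difference at 80% power = (1.960 + 0.842) × √(1/n₁ + 1/n₂). All infants (491 and 491): 0.18 SD. AD infants only (118 and 82): 0.40 SD, about 2.2 times as large. This uses a normal approximation with the same SD in infants with and without AD.

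**5. The part of the effect that would be lost**

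If AD adds d disturbed nights a week, prevention contributes (0.24 − 0.168) × d = 0.072d nights per infant to the whole-cohort contrast. The documents give no value for d. Assuming d = 1 to 2, this is 0.07 to 0.14 nights. Among AD infants only, this component is zero by construction.

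**The case against.** The strongest reply is that this is a mislabelled source and nothing more. Table 3, the protocol contact lists, protocol 2.2.2 and Table 4 all agree that sleep is collected from everyone, and the point arithmetic suggests that a general sleep question was filed in the IDQOL list by mistake. On that reading the data exist for all infants, and neither the loss of numbers nor the selection occurs. This largely stands, and it is why the point is minor. It does not remove the conflict: 5.1 is the section that 5.4 names for definitions, and the documents do not show how the survey branches.

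Three stronger inferences are tempting and are not supported.

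- A reader might infer that the endpoint exists only in infants with AD. The schedule and Table 4 contradict that.
- A reader might infer that the group is selected by the primary outcome. IDQOL is triggered by logic in the parent survey, whereas the primary outcome is a chart-abstracted, adjudicated provider diagnosis, so the two groups need not coincide.
- A reader might infer that missing sleep values in infants without AD would be imputed from those with AD. SAP 3.6 mentions imputation of missing outcomes in general terms, but the method in 5.9 is written for the primary outcome and no imputation model for sleep is given.

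**Conclusion.** Wrong as written, and minor: one secondary endpoint carries a source label that conflicts with the plan's own schedule and analysis population. The conflict is certain from the text. The harm is conditional. It arises only if item 11 is applied literally or if the nights question was programmed inside the AD branch of the questionnaire, and the schedule makes the second unlikely without ruling it out.

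In that case about a fifth of the cohort would contribute, and the comparison would miss any sleep benefit through AD prevention. The figure of 200 of 982 uses two-year planning risks of provider-diagnosed AD as a stand-in for the survey trigger. It does not describe the 12-month assessment. The nights-per-infant range rests wholly on the assumed value of d.

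**What to change.** In SAP 5.1 item 11 and 5.4 item 10:

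- Keep the 0-7 nights wording now printed in item 9b, but present it as the sleep-loss question asked of all participants at 12 and 24 months. Removing it with the IDQOL reference would leave the endpoint with no wording at all.
- Delete the attribution to IDQOL.
- State the ITT population, as Table 4 already does.

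In item 9b, take the nights question out of the IDQOL list, and settle whether the 0-4 severity item counts, so that the items add up to the stated 30 points.

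Before data lock, confirm in the REDCap questionnaires that the nights question lies outside the AD branch. If it lies inside, the plan should say that the endpoint was observed only in infants with AD and describe the comparison accordingly.

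The cost is a few sentences of SAP text and one check of the survey form. No new data collection is needed if the schedule was followed.

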5.2. Definitions for Subpopulation Analyses

In **exploratory analyses** we will investigate potential differences in treatment effect in subgroups with known or hypothesized risk or protective associations with AD using the approach given in section 5.5 below. The subgroups to be investigated are:

1. **Family history of atopy in a first-degree relative**, associated with approximately doubled risk of AD¹³⁻¹⁶ and expected in 40 to 60 percent of the population, as found in our planning grant and suggested in other studies of IgE sensitization in the population¹⁷. This is one of

our stratification variables for randomization. If the elevated risk in this population is explained by filaggrin gene mutations affecting the skin barrier, then emollient use should be most protective in babies with a family history of atopy; this would point to recommending daily emollient use only in this high-risk population.

We will treat this as a binary variable (*yes* vs *no/don't know*) to the following question:

Has at least one of your baby's blood-related PARENTS, BROTHERS OR SISTERS ever been diagnosed with asthma, eczema (atopic dermatitis) or hay fever (seasonal allergies)?

2. **Dry climate**, which we will measure using the average relative humidity over a year for the clinic's locality in records from the National Climate Data Center and Weather Service. More detailed methods will be developed, following the general approach in previous work, where a protective effect of RR 0.8 was observed in the highest humidity areas¹⁸. If emollient prevents AD by preserving the skin barrier, then the treatment effect should be greatest in low-humidity areas.
3. **Having pets or regular contact with farm animals at baseline**. Meta-analysis has found a protective effect for exposure to dogs (RR 0.72) and pets overall (RR 0.75), with more equivocal evidence for exposure to cats (RR 0.94)¹⁹. We expect about 30% of participants to own cats and 40% to own dogs based on large national pet ownership surveys. This analysis will be conducted in two steps. The first step will use a set of indicator variables for the following yes/no questions, and the second will use an overall binary variable for any regular contact with animals:

Does your baby have regular (at least weekly) contact with farm animals?

Does your family own one or more dogs?

Does your family own one or more cats?

It is possible that farm animal contact will be collinear with other pets (babies with contact with farm animals may usually also have contact with both cats and dogs). In that case, the design variables may be coded as cats and dogs exclusive of farm animals.

Because dogs, and pets in general, are protective, the treatment effect should be greater in families without pets, and/or with cats relative to dogs and other pets.

4. Treatment effect of **CeraVe** cream or ointment (at any time) vs all other emollients in the treatment arm vs controls. A study published since the start of this trial suggests that previously observed benefits from regular emollient use may be attributable to ceramides. Ceramides are present in both CeraVe cream and ointment, which is among the choices for study treatments. Although we are not powered to detect a significant difference from ceramide-containing emollients versus others, we plan to investigate whether use of these products is associated with a reduction in AD. The planned design variables for this analysis are for ceramides (1=CeraVe cream or ointment, 0=otherwise) and other emollients in the treatment arm (1=used, 0=not used). Controls will be used as the reference group.
5. The **baby's age at randomization** may moderate treatment effects, in that emollient use may be most protective if initiated early. Depending on the distribution of ages, this variable will be evaluated as age in days, or if needed, as a categorical variable for early vs late recruitment.
6. More **frequent bathing** may affect the skin barrier and change the treatment effect. Enhance because frequent bathers have more skin barrier damage. Reduce effect because emollient is not potent enough to overcome frequent bathing damage. Frequency of bathing is reported in days per week. This may be analysed as an ordinal variable or as a binary variable with the split determined by existing evidence.

7. **Caesarean birth** may affect the skin microbiome and modify the known effects of emollient on skin microbiome and barrier protection, though the direction of the effect is difficult to hypothesize.

In addition, **subgroup analyses by sex/gender and race and/or ethnicity** are required under the Inclusion of Women and Minorities policy of the NIH (NOT-OD-18-014). Coding for these variables will be as follows:

8. **Sex** of the baby will be coded as male/female; gender non-binary is not assessed. We have no a priori hypothesis about a differential treatment effect for biological sex.
9. **Race** will be coded using a set of design variables for the check-all-that-apply responses. African American race is associated with higher prevalence of atopic conditions, but lower prevalence of filaggrin defects. Thus, in spite of the elevated risk of eczema, we expect the treatment will likely be less effective for African American compared to other babies, because the mechanism of preserving the skin barrier would contribute less in this subpopulation. The source variable is coded as follows:

What is your baby's race?(please check all that apply)

American Indian or Alaska Native

Asian

Black or African American

Native Hawaiian or other Pacific Islander

White

Other

Prefer not to answer

10. **Hispanic ethnicity** will be treated as a binary variable, with "prefer not to answer" treated as missing, unless >10% of responses are missing, in which case ethnicity will be coded with two design variables, (1=Hispanic/0=not, 1=missing/0=present) based on the following question:

What is your baby's ethnic group?

Hispanic or Latino

Not Hispanic or Latino

Prefer not to answer

